##### **Primary**

- To evaluate the efficacy of the combination of ABI-009 and pazopanib at the RP2D.

##### **Secondary**

- To evaluate the safety profile and to further evaluate the efficacy of nab-Sirolimus plus pazopanib combination therapy

##### **Exploratory**

- To study the correlation of clinical outcomes with Next Generation Sequencing and Immunohistochemical analyses of tumor biomarkers, including baseline secreted protein acidic and rich in cysteine (SPARC) expression.
- To assess baseline tumoral immune parameters, including PD-1, PD-L1, mutational burden, and infiltrating lymphocytes, in correlation with clinical outcomes.

### 2.2. Endpoints

#### Endpoints in Phase 1

##### **Primary Endpoint**

- Dose-limiting-toxicities, as defined in Section 6.4

##### **Secondary Endpoints**

- Adverse Events profile (based on National Cancer Institute [NCI] Common Terminology Criteria for Adverse Events [CTCAE] v5.0) of all subjects and each dose cohort

#### Endpoints in Phase 2 – Data from both phase 1 and 2

##### **Primary Endpoint**

- Progression-free survival rate at 3 months, based on Response Evaluation Criteria in Solid Tumors (RECIST) v1.1

##### **Secondary Endpoint**

- Adverse Events profile (based on NCI CTCAE v5.0)

- Median PFS, PFS rate at 6 months, based on RECIST v1.1
- Median OS, OS at 12 months
- Objective response rate based on RECIST v1.1
- Disease control rate, defined as CR plus PR plus SD  $\geq 18$  weeks, based on RECIST v1.1
- Duration of response

### Exploratory endpoints

- Optional pre-treatment tumor tissue collection (fresh or archival) for biomarker analysis:
  - Correlation of genetic profiling and tissue biomarker analysis with clinical benefit
  - Correlation of baseline SPARC expression with clinical benefit
  - Correlation of baseline immune parameters with clinical benefit

### 2.3. Study Design

This is an open label, dose-finding, single-arm, prospective phase 1/2 study to identify the RP2D of nab-Sirolimus given IV on either Day 1 and Day 8, or Day 1 only of a 21-day cycle (q2/3w), plus daily oral pazopanib in subjects with advanced nonadipocytic STS. The target DLT rate is  $\leq 20\%$ .

The study will be conducted in compliance with International Conference on Harmonisation (ICH) Good Clinical Practices (GCPs).

#### Dose-finding Phase 1 Portion of the Study:

Dose levels of nab-Sirolimus will be tested in cohorts of 3 subjects each using the 3+3 dose-finding design. Potential doses of nab-Sirolimus are contained below in Table 1 and Table 2. All cohorts in Table 1 are considered completed. As of this amendment, new enrollments will follow the cohort schedule in Table 2.

**Table 1. Day 1 and Day 8 Dosing Levels (Closed/Completed Cohorts)**

Dose Levels (Day 1 and Day 8 Dosing)	Protocol Version Added	Planned Starting Dose of ABI-009 in mg/m 	Planned Starting Dose of Pazopanib in mg
-2	1.0	30	800
-1	1.0	45	800
0	1.0	60	800
1	1.0	75	800
2	1.0	100	800
0B	3.0	60	400
1B	3.0	75	400
2B	3.0	100	400
-1B	3.0	45	400
-2B	3.0	30	400

**Table 2 - Day 1 Only Dosing Levels (Amendment 3, Version 4.0 and Later Only)**

Dose Levels (Day 1 Only Dosing)	Planned Starting Dose of ABI-009 in mg/m 	Planned Starting Dose of Pazopanib in mg
-2C	15	400
-1C	20	400
0C	30	400
1C	45	400
2C	60	400
3C	75	400
4C	100	400

After enrollment of the first 3 dose cohorts (0, -1, and -2) an RP2D had not yet been identified. DLTs were observed in all three of these enrolled cohorts. A total of 16 subjects were consented resulting in 13 enrollments and 3 screen failures. DLTs were observed at all dose levels. A summary of DLTs observed in Cohorts 0, -1, and -2 are provided below in Table 3. Of the 13 subjects enrolled, 11 subjects had nab-Sirolimus and/or pazopanib dose reduced, and three subjects discontinued due to toxicity.

**Table 3 - Summary of DLT (Combined Cohorts 0, -1, -2)**

Dose Limiting Toxicity	Occurrences
Platelet Count Decrease	8
WBC/Neutrophil Count Decrease	3
Lipase Increase	2
Proteinuria	1
Urinary Tract Infection	1
Mucositis, Oral	1
Alanine Aminotransferase Increase	1

Starting dose of pazopanib must remain consistent within each cohort but may be adjusted during treatment as needed due to toxicity. Protocol Amendment 3 added the option for additional cohorts, and modified the dosing schedule from Day 1/8 to Day 1 only of a 21-day cycle as summarized in Table 1 and Table 2. The starting dose began at 30 mg/m^2 of nab-Sirolimus on Day 1 and pazopanib at 400 mg daily (Cohort 0C). Starting with Amendment 3, the dose finding portion of the study was re-initiated, enrolling 3 subjects at 30 mg/m^2 of nab-Sirolimus and 400 mg of pazopanib with Day 1 dosing only. Cohort 0C and subsequent cohorts followed the same dose-finding and DLT rules outlined below.

The dose levels of nab-Sirolimus will be tested in cohorts of 3 subjects each using the 3+3 dose-finding design. The starting doses for each cohort and potential escalation or de-escalation are

summarized in Table 1 and Table 2. If no DLT is observed during the first 2 cycles at the starting dose in the first 3 subjects, the next dose cohort would enroll subjects at the next highest dose level. If no DLT is observed at the first 3 subjects at the higher dose level, the next dose cohort would continue to escalate to the next highest dose level, up to a maximum of 100 mg/m^2. If 1 DLT is observed any dose cohorts in the first 3 subjects, then the cohort will expand, and an additional 3 subjects will be enrolled at that dose level. The first three subjects in a given cohort must complete the DLT window prior to expanding to include the additional 3 subjects. If ≤1 of 6 subjects experience a DLT at the starting dose or higher, enrollment would continue to the next higher dose level.

If ≥2 subjects experience a DLT at dose level higher than the starting dose, enrollment will be discontinued for that dose cohort and the previous dose level would be declared the MTD. If ≥2 subjects experience a DLT at the starting dose of a given cohort, further enrollment at that dose level will be discontinued and nab-Sirolimus will be reduced to the next planned dose level, to a lower limit dose level of 15 mg/m^2. The MTD of nab-Sirolimus combined with pazopanib is the highest nab-Sirolimus dose level at which ≤1 of 6 (or 0 out of 3) subjects experienced a DLT, thus a target DLT rate of roughly 17%. RP2D is identified based of the totality of safety and efficacy data.

### **Phase 2 Portion of the Study:**

This will be conducted using a Simon's two-stage design. Subjects enrolled in the phase 1 study at the RP2D cohort will be included for response and safety evaluation in phase 2.

#### **2.4. Study Duration, End of Study, End of Treatment, End of Treatment Visit, Follow-up Period**

The study is expected to take approximately 36 months from first subject enrolled to last subject follow-up, including approximately 30 months of enrollment period, an estimated 6 months of treatment (or until treatment is no longer tolerated).

End of Treatment (EOT) for a subject is defined as the date of the last dose of nab-Sirolimus or pazopanib, whichever is later. Single agent continuation of nab-Sirolimus is permitted. If a subject must discontinue nab-Sirolimus treatment, they will be discontinued from the study. End of Treatment Visit for a subject is when safety assessments and procedures are performed after the last treatment of nab-Sirolimus or pazopanib, whichever is later (+/- 3 days).

The 30-Day Follow-Up Visit for a subject is defined as the date when safety assessments and procedures are performed after the End of Treatment visit. The 30-Day Follow-Up visit should occur 30 days (+/- 7 days) after the last dose of nab-Sirolimus or pazopanib, whichever is later.

The End of Study (EOS) defined as either the date of the last visit of the last subject to complete the study, or the date of receipt of the last data point from the last subject that is required for primary, secondary, and/or exploratory analysis, as pre-specified in the protocol.

Follow-up period is the on-study time period after the 30-Day Follow-Up Visit. All subjects that discontinue study drug and have not withdrawn full consent to participate in the study will continue in the follow-up phase for survival and initiation of new anticancer therapy. Follow up will continue approximately every 12 weeks from the 30-Day Follow-Up Visit (±3 weeks), until

death, withdrawal of consent, or the study closes, whichever is the earliest. This evaluation may be made by record review and/or telephone contact.

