End of Study	Either the date of the last visit of the last subject to complete the study, or the date of receipt of the last data point from the last subject that is required for primary, secondary, and/or exploratory analysis, as pre-specified in the protocol.
Follow-up Period	The on-study time period after the 30-Day Follow-Up Visit. All subjects that discontinue study drug and have not withdrawn full consent to participate in the study will continue in the follow-up phase for survival and initiation of new anticancer therapy. Follow up will continue approximately every 12 weeks ( $\pm 3$ weeks) from the 30-Day Follow-Up Visit, or more frequently as needed, until death, withdrawal of consent, or the study closes, whichever is the earliest. This evaluation may be made by record review and/or telephone contact.
Primary Analysis	For this study will occur after all subjects have either completed the study or completed 12 months of treatment. Subjects who are still active at the time of the primary analysis may continue on study until disease progression or medication intolerance is observed.
Efficacy Analysis Dataset	All enrolled subjects with measurable tumor per RECIST v1.1 at baseline who received at least 2 doses of ABI-009 and had a follow-up CT / MRI (modified treated population).

Full Analysis Set	All enrolled subjects who receive at least 1 dose of ABI-009 (treated population).
Per-protocol Analysis Set	All enrolled subjects who do not have any prospectively defined protocol violations.
Progression-free survival	The time from the first dose date to the first observation of a disease progression or death due to any cause.
Overall survival	The time from the first dose date to the date of death due to any cause.
Overall response rate	The proportion of subjects who achieve a confirmed partial response or complete response per RECIST v1.1. Response rates based on a local radiologic assessment.
Duration of response	The time from when criteria of response are first met until the first observation of disease progression per RECIST v1.1 or death due to any cause, whichever comes first.

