## **5.6. Follow-up Period for Survival and Initiation of Anticancer Therapy**

Post-treatment survival time and any subsequent anticancer therapy information status will be monitored approximately every 12 weeks ( $\pm 3$  weeks) from 30-Day Follow Up Visit or more frequently as needed, until death, withdrawal of consent, or the study closes, whichever is earliest. This evaluation may be by record review and/or telephone contact.

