### **11.2. Discontinuation from the Study**

The following events are considered sufficient reasons for discontinuing a subject from the study:

- Withdrawal of consent
- Death
- Lost to follow up
- Protocol violation
- Other (to be specified on the CRF)

The reason for study discontinuation should be recorded in the CRF and in the source documents.

At the time of withdrawal, it should be determined whether the subject is withdrawing from treatment alone, or from treatment and collection of further data (e.g., survival). Every effort should be made to collect survival data after subject withdraws from treatment.

Subjects have the right to withdraw from the study at any time and for any reason without prejudice to his or her future medical care by the physician or at the institution.

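### Section 2.4 takes a subject who must stop nab-Sirolimus out of the study, which contradicts the protocol's own survival and safety follow-up rules and, read literally, loses OS data

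*Combined protocol and SAP*

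**What the plan says.** Section 2.4 contains two rules for a subject who stops nab-Sirolimus. The first is "If a subject must discontinue nab-Sirolimus treatment, they will be discontinued from the study". The second, three paragraphs later, is "All subjects that discontinue study drug and have not withdrawn full consent to participate in the study will continue in the follow-up phase", which covers survival and the start of new anticancer therapy. The definitions list describes that follow-up period as "The on-study time period after the 30-Day Follow-Up Visit", so a subject in it is still on study.

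Other sections side with the second rule. Section 5.6 runs survival follow-up "until death, withdrawal of consent, or the study closes, whichever is earliest", and Section 9.3 has the same end points. Section 11.2 separates leaving treatment from leaving data collection and adds: "Every effort should be made to collect survival data after subject withdraws from treatment". Section 11.1 treats intolerable adverse events as a reason to leave the investigational product.

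Two further provisions bear on the sentence. Section 2.4 also says: "End of Treatment (EOT) for a subject is defined as the date of the last dose of nab-Sirolimus or pazopanib, whichever is later". Sections 5.4 and 9.2 call for a safety visit about 30 days after the last dose of protocol therapy and adverse event recording for 30 days after it.

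**The concern.** Both rules in Section 2.4 cannot be followed for the same subject, and the trigger is foreseeable: Tables 9 and 11 and Section 6.1.3.1 each name toxicities for which nab-Sirolimus is stopped permanently. A site that follows the first rule closes the subject's participation at that point. Median OS and OS at 12 months are secondary endpoints, and PFS counts death from any cause, so deaths after such an exit would go unrecorded for both.

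Subjects who stop for toxicity may have a different prognosis from those who stay on drug. Kaplan-Meier estimation (Section 9.3) treats censored subjects as having the same future risk as those still observed, so removing this group could bias the estimates. The direction cannot be told from the documents.

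**Working it through.** The plan gives no figure for loss to follow-up, so the check is mainly a comparison of provisions, followed by a scale estimate.

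**Step 1. Literal effect of the sentence on each provision.**

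| Provision | What it requires after nab-Sirolimus stops | Effect of study exit |
|---|---|---|
| Definitions; Sections 2.4 (follow-up paragraph), 5.6, 9.3 | Survival contact about every 12 weeks | Ended |
| Section 11.2 | Effort to obtain survival data after treatment withdrawal | Contradicted |
| Sections 5.4, 9.2 | 30-day visit and 30 days of adverse event recording | Ended |
| Section 2.4, End of Treatment | Date set by the later drug, so pazopanib may run on | Contradicted |

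**Step 2. What the sentence does to scans.** The provisions that end scheduled imaging differ:

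- Section 5.2.4: progression or unacceptable toxicity.
- Tables 4 and 5, footnote k: progression or last treatment.
- Section 9.3: end of treatment.

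Sections 5.2.4 and 5.3 add one scan at the End of Treatment visit for subjects who stop for a reason other than progression. The follow-up phase after that covers survival and new therapy only, with no imaging.

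- *Both drugs stopped for toxicity:* scheduled scans end under all three provisions, whatever Section 2.4 says.
- *Nab-Sirolimus stopped, pazopanib continuing:* footnote k and Section 9.3 would keep scans going, because treatment has not ended. Here the sentence itself ends them.

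**Step 3. Scale.** Inputs: 3 of the first 13 subjects stopped therapy for adverse events (Sections 1.5 and 2.3); phase 2 total of 39 (Sections 3.1 and 9.5).

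- Observed rate: 3/13 = 0.231, or 23%.
- Exact (Clopper-Pearson) 95% limits: lower = 2.5% quantile of Beta(3, 11) = 0.050; upper = 97.5% quantile of Beta(4, 10) = 0.538.
- Applied to 39: 0.231 × 39 = 9.0; 0.050 × 39 ≈ 2; 0.538 × 39 ≈ 21.

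The range of 2 to 21 reflects sampling uncertainty only. The 13 subjects were in cohorts 0, -1 and -2, on Day 1/Day 8 dosing with an 800 mg pazopanib starting dose. New subjects receive nab-Sirolimus on Day 1 only with 400 mg. The documents say these 3 stopped therapy, not nab-Sirolimus specifically, and do not say when.

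**The case against.** The strongest reply is that this is loose wording and not a planned loss of data. The sentence directly follows one permitting nab-Sirolimus to continue as a single agent, so it may be meant as the converse rule about treatment. Survival follow-up is required in several places and has its own column in Tables 4 and 5. A site would have to let one sentence override all of them, and Section 13.3 lets investigators search public records for survival status when a subject withdraws. The list in Section 11.2 has an open category for other reasons, so it does not by itself rule out the Section 2.4 exit.

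Most of this stands as a reason to expect that many sites would keep following subjects. It does not remove the contradiction: the sentence says study, not study treatment. Table 9 uses similar language for unresolved grade 3 noninfectious pneumonitis, where subjects are withdrawn from the study, so a literal reading is not far-fetched.

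A reader might also infer that the sentence costs the trial its PFS data, including the 3-month primary endpoint, for everyone who stops for toxicity. The documents do not support that. Step 2 shows that scheduled imaging already ends for subjects who stop both drugs for toxicity, with an End of Treatment scan to record status at stopping. Only stops before about 3 months could touch the primary endpoint, and Section 9.5 replaces subjects who have no follow-up scan.

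**Conclusion.** The contradiction is established from the text, within Section 2.4 and against the definitions and Sections 5.4, 5.6, 9.2, 9.3 and 11.2. It is an operative rule that conflicts with the rest of the plan, not a missing detail. If applied literally, it loses three things for subjects who stop nab-Sirolimus for toxicity: survival data for median and 12-month OS, later deaths that would count as PFS events, and the 30-day safety follow-up. It also ends scans where pazopanib outlasts nab-Sirolimus. Whether the loss would bias OS depends on how the prognosis of these subjects differs, which the documents do not show.

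The number affected is not known. A reader might take 9 of 39 as a forecast. It is only the point estimate from 13 subjects on a different schedule and pazopanib starting dose, with no stated timing, and it assumes that the rate carries over and that the sentence is enforced.

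**What to change.** Reword the sentence in Section 2.4 so that stopping nab-Sirolimus does not end study participation. State that such subjects have the 30-day safety visit and enter survival follow-up unless they withdraw consent. The cost is one sentence in an amendment, because that follow-up is already planned.

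Two related items should be handled alongside it:

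- Reconcile the sentence with the End of Treatment definition, which allows pazopanib to run past nab-Sirolimus. What happens to pazopanib is the sponsor-investigator's decision, and the new wording should not settle it by implication.
- Reconcile the scan-end wording in Section 5.2.4, footnote k of Tables 4 and 5, and Section 9.3 with one another and with the PFS definition, which is not limited to time on drug. The one-sentence edit does not supply imaging after all treatment has stopped. Any scans added for that purpose would be an extra cost.

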### **3. STUDY POPULATION**

#### **3.1. Number of Subjects**

**Phase 1:** up to 49 subjects to identify the MTD, but the MTD may be reached with as few as 22 subjects. Subjects who discontinue from the study prior to completing the DLT assessment window for reasons other than toxicity will be replaced at the same dose level.

**Phase 2:** In the first stage, at least 23 subjects would be enrolled, including the 3-6 subjects from phase 1 at the RP2D. If at least 11 were progression-free at the 3 months evaluation, then additional subjects would be enrolled to a total of 39 subjects in the Phase 2.

#### **3.2. Inclusion Criteria**

A subject will be eligible for inclusion in this study only if all the following criteria are met during screening:

1. Subjects,  $\geq 18$  years old, must have a histologically confirmed diagnosis of nonadipocytic STS that is either metastatic or locally advanced and for which curative therapy is not available, surgery is not a recommended option, and pazopanib treatment is indicated.
2. Subjects must have one or more measurable target lesions by RECIST v1.1, assessed via CT scan or MRI.
3. Clinical or radiological progression or failure due to toxicity on at least 1 prior regimen of systemic treatment for advanced disease. Subjects may not have received more than 4 prior lines of systemic therapy (no more than 2 prior therapies may be combination cytotoxic therapies). Neo-adjuvant/adjuvant/maintenance treatments are not included for this criterion.
4. Last dose of prior therapy must have been completed a minimum of 14 days prior to start of protocol therapy. All ongoing toxicities related to prior therapy must be resolved or grade 1 (except alopecia).
  - a. NOTE: Toxicities from prior therapy that have resolved with sequelae (e.g. hypothyroidism) and are asymptomatic or well-controlled are not exclusionary.
5. Subjects must have adequate organ function and blood chemistry and blood count parameters:
  - a. Total bilirubin  $\leq$  upper limit of normal (ULN) mg/dL (Subjects with known Gilbert's Syndrome and a Total Bilirubin  $\leq 3$  mg/dL are permitted to enroll to Phase 2/expansion phase only with sponsor-investigator approval)
  - b. AST  $\leq 2.5 \times$  ULN and ALT  $\leq 2.5 \times$  ULN
  - c. Serum creatinine  $\leq 1.5 \times$  ULN (If serum creatinine is  $>1.5$  mg/dL, calculated creatinine clearance  $>50$  mL/min using the Cockcroft-Gault formula may be included)
  - d. Absolute neutrophil count (ANC)  $\geq 1.5 \times 10^9/L$ ;
  - e. Platelet count  $\geq 100,000/mm^3$  ( $100 \times 10^9/L$ );
  - f. Hemoglobin  $\geq 9$  g/dL
  - g. Serum triglyceride  $\leq 300$  mg/dL; serum cholesterol  $\leq 350$  mg/dL.

6. Baseline cardiac left ventricular ejection fraction (LVEF) within institutional limits of normal (by echocardiogram or MUGA study).
7. Baseline electrocardiogram with QTc <480 millisecond (Bazett's).
8. Eastern Cooperative Oncology Group (ECOG) performance status 0 or 1.
9. Male or non-pregnant and non-breast feeding female:
  - a. Females of child-bearing potential must agree to use highly effective contraception without interruption from initiation of therapy and while on study medication and have a negative serum pregnancy test ( $\beta$  -hCG) result at screening and agree to ongoing pregnancy testing during the course of the study, and at the end of study treatment. A highly effective method of contraception is defined as one that results in a low failure rate (that is, <1% per year), when used consistently and correctly, such as implants, injectables, combined oral contraceptives, some intrauterine contraceptive devices, sexual abstinence, or a vasectomized partner (Appendix 1).
  - b. Male subjects must practice abstinence or agree to use a condom during sexual contact with a pregnant female or a female of childbearing potential while participating in the study (Appendix 1).
10. Life expectancy of >3 months, as determined by the investigator.
11. Ability to understand and sign informed consent.
12. Willingness and ability to comply with scheduled visits, laboratory tests, and other study procedures.

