g For all female subjects of childbearing potential (see Inclusion 5), a serum pregnancy test will be done at screening. A serum or urine pregnancy test will be repeated within 72 hours before first treatment if the serum pregnancy test occurred  $>72$  hours before dosing, and at EOT and 30-Day Follow-Up (if applicable). Pregnancy tests conducted after screening will be recorded in the source documentation only.

h Single tracing ECG and lipids evaluations are every even cycle (C2, C4, C6, etc.). Only lipid panel at baseline is required to be fasting lipid.

i Height is measured only at C1D1. BSA is calculated ONLY on C1D1; to be recalculated only if the weight changes by  $> 10\%$  in subsequent cycles, at which point the recalculated weight will become the new baseline. Vitals signs to include respiration rate, temperature, systolic/diastolic blood pressure, and pulse. Vital signs to be collected Pre-Dose (within 15 minutes prior to start of infusion) and Post-Dose (+10 minutes from end of infusion).

j Rapamycin levels are done locally and for all subjects in Phase 1 at Cycle 1 D8 prior to infusion (within 15 minutes prior to infusion) and on D15 (any time) to assess trough levels as well as in Cycle 2, D1 and D8 prior to infusion and on Day 15 (anytime).

k Baseline scans should be done within 4 weeks of C1D1, preferably as close to first treatment as possible. Every 6 weeks from C1D1 ( $\pm 1$  week) for the first year, then every 12 weeks ( $+/- 1$  week) until disease progression or last treatment, regardless of missed or out of window doses. End of Treatment Visit CT/MRI should be performed only for those subjects that discontinue treatment for a reason other than disease progression. All responses must be confirmed by an additional CT scan after 6 weeks. MRI may be used if CT is contra-indicated for a subject. The same mode of imaging at screening must be used consistently throughout the study.

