Adverse Event Assessment		Continuous from time of consent to 30 days after last study drug					
Survival Assessment							x

a All visits are allowed to occur in a window of  $\pm 3$  days unless otherwise specified.

b Baseline screening visit will be done within 28 days prior to study treatment Day 1. Baseline scans should be completed within 28 days of C1D1, as close to C1D1 as possible.

c Day 15 visit is only in Cycle 1 and 2. Cycle 3+ does not have a Day 15 visit.

d End of Treatment-phase (EOT) Visit should be within  $\pm 3$  days of last study treatment.

e Thyroid function test to be repeated as needed, based on investigator's opinion.

f Subjects who consent for pre-treatment tissue collection for biomarker analysis: either fresh-frozen or formalin-fixed paraffin-embedded (FFPE) tumor blocks or unstained slides (min 10). Fresh tissue collection may only be obtained if clinically feasible and without undue risk to the subject.

g For all female subjects of childbearing potential (see Inclusion 5), a serum pregnancy test will be done at screening. A serum or urine pregnancy test will be repeated within 72 hours before first treatment if the serum pregnancy test occurred  $>72$  hours before dosing, and at EOT and 30-Day Follow-Up (if applicable). Pregnancy tests conducted after screening will be recorded in the source documentation only.

h Single tracing ECG and lipids evaluations are every even cycle (C2, C4, C6, etc.). Only lipid panel at baseline is required to be fasting lipid.

i Height is measured only at C1D1. BSA is calculated ONLY on C1D1; to be recalculated only if the weight changes by  $> 10\%$  in subsequent cycles, at which point the recalculated weight will become the new baseline. Vitals signs to include respiration rate, temperature, systolic/diastolic blood pressure, and pulse. Vital signs to be collected Pre-Dose (within 15 minutes prior to start of infusion) and Post-Dose (+10 minutes from end of infusion).

j Rapamycin levels are done locally and for all subjects in Phase 1 at Cycle 1 Day 1 Post-Dose (within +10 minutes from end of infusion), Cycle 1 Day 1 – 24-hour Post-Dose (optional, +/- 2 hours), Cycle 1 Day 8 and Day 15 anytime, as well as in Cycle 2 Day 1 Pre-Dose (within 15 minutes prior to infusion) and on Cycle 2 Day 8 and Day 15 (anytime).

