### **5.2.1. Day 1 Assessment**

The following assessments will be performed on Day 1 of each cycle, unless otherwise specified:

- Physical examination
- Weight assessment
- Height assessment (only in C1)
- Concomitant medication and procedures evaluation
- Vital signs (temperature, sys/dias blood pressure, respiration rate, and pulse)
- ECOG performance status
- CBC with differential
- Clinical chemistry panel
- ECG and lipid panel (every even visit, i.e. C2, C4, etc.)
- Urinalysis
- Adverse Event assessment
- Rapamycin levels (only in Phase 1, C1 and C2)
- 60-minute observation window post end of infusion for Cycle 1. If a subject completes Cycle 1 with no infusion related reactions, the observation period may be omitted for Cycle 2 and onwards. If at any time the subject experiences an infusion related reaction, the 60-minute post-dose observation period will be reinstated.

All Day 1 evaluations for Cycle 1 may be omitted if screening evaluations are performed within 72 hours of Cycle 1 Day 1. All Day 1 laboratory assessments and physical examination for Cycle 2+ may be performed up to 72 hours prior to planned treatment.

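### Inclusion 9a commits women of child-bearing potential to pregnancy testing during the study, but the schedule has no routine test between the first dose and End of Treatment

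*Combined protocol and SAP*

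**What the plan says.** Section 3.2, criterion 9a, asks three things about testing from women of child-bearing potential: a negative serum result at screening, and then that they "agree to ongoing pregnancy testing during the course of the study, and at the end of study treatment". Testing during the study is thus listed apart from both the screening test and the end-of-treatment test.

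The timing is set in Tables 4 and 5 (Section 4). In both, the pregnancy-test row is marked at Baseline Screening, the EOT Visit and the 30-Day Follow-Up Visit. The Day 1, Day 8 and Day 15 cells are empty. Footnote g has the same text in both tables. It opens with "For all female subjects of childbearing potential (see Inclusion 5), a serum pregnancy test will be done at screening". It continues with "A serum or urine pregnancy test will be repeated within 72 hours before first treatment if the serum pregnancy test occurred" more than 72 hours before dosing, and ends the list of timepoints with "and at EOT and 30-Day Follow-Up (if applicable").

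Inclusion 5, to which footnote g points, begins "Subjects must have adequate organ function and blood chemistry and blood count parameters" and does not concern child-bearing potential.

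**The concern.** Sites work from the schedule tables and the visit lists. A site that follows them exactly would do no routine pregnancy test while the subject is receiving nab-sirolimus and daily pazopanib, although the subject has agreed to such testing as a condition of entry. An early pregnancy without symptoms could then go unnoticed while dosing continues. What is at stake is subject safety and the consistency of the protocol. Sample size, error rates, power and the primary endpoint are not involved.

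**Working it through.** The protocol states no figure on this point to reproduce. The check sets the commitment beside each place where a test could be scheduled, then counts.

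**Where tests are and are not scheduled**

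| Source | Pregnancy test? | Timing relative to dosing |
|---|---|---|
| Section 5.1; Tables 4 and 5, screening column | Yes, serum | Before first dose |
| Footnote g, repeat within 72 hours | Conditional, serum or urine | Before first dose |
| Section 5.2.1, Day 1 list | No | On treatment |
| Section 5.2.2, Day 8 list | No | On treatment |
| Section 5.2.3, Day 15 list (Cycles 1 and 2) | No | On treatment |
| Section 5.3, EOT list | Yes | After last dose |
| Section 5.4, 30-Day list | Yes | After last dose |

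Three other places might have filled the gap, and none does:

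- Table 6 puts the pregnancy test under Other Labs. The urinalysis done on Day 1 therefore does not include it.
- Appendix 1 tells women who choose abstinence to keep having tests according to the study calendar, which refers back to the same tables.
- Section 10.5 covers reporting of, and monitoring for, pregnancies. It sets no test.

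**Count.** Routine tests after first dose and before EOT: 0 under Table 4 and 0 under Table 5.

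**Infusions given without a scheduled test**

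Inputs: a 21-day cycle (Section 2.3) and a treatment duration in Section 2.4 of "an estimated 6 months of treatment (or until treatment is no longer tolerated"). Assumptions: 6 months is 26 weeks, and no cycle is delayed.

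- 26 weeks / 3 weeks per cycle = 8.7, so eight full cycles and part of a ninth.
- Day 1 falls at weeks 0, 3, 6, 9, 12, 15, 18, 21 and 24, which is 9 Day 1 infusions.
- The first is covered by the screening test or its 72-hour repeat: 9 − 1 = 8 Day 1 infusions (Cycles 2 to 9) with no scheduled test.

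The count depends on time on treatment. Under the same assumptions it is the whole-number part of weeks/3:

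| Time on treatment | Weeks / 3 | Day 1 infusions after Cycle 1 |
|---|---|---|
| 3 months (13 weeks) | 4.3 | 4 |
| 6 months (26 weeks) | 8.7 | 8 |
| 12 months (52 weeks) | 17.3 | 17 |

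The documents do not say how many women of child-bearing potential are expected, so the number of subjects affected cannot be given.

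**The case against.** The strongest reply is that 9a is an agreement criterion with no stated interval. It speaks of the course of the study, not of treatment or of each cycle. The calendar does hold two tests that are neither the screening test nor the EOT test: the conditional repeat before the first dose and the 30-Day Follow-Up test. Appendix 1, at least for women choosing abstinence, equates continued testing with whatever the calendar says. On that reading the calendar could satisfy 9a as written.

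This reading is possible but strained. The repeat comes before any exposure, and only if the screening test is too old. The 30-Day test comes after the last dose. Neither can detect a pregnancy while dosing continues, which is the natural purpose of *ongoing* testing listed apart from the end-of-treatment test.

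Other points on that side stand in part:

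- **Other safeguards exist.** These are highly effective contraception, a negative test before the first dose, examination and adverse-event assessment at visits, and the Section 10.5 instruction to monitor for and report pregnancies. They narrow the gap without closing it. Section 8.1 itself urges great caution with hormonal contraceptives because possible enzyme effects on hormone metabolism are unknown.
- **The figure of 8 is not a count of breaches.** The protocol nowhere requires one test per cycle. The figure describes how many infusions go by without a scheduled test. Delays or early stopping lower it, and delays were common on the earlier schedule: Section 1.5 reports missed Day 8 or delayed Day 1 doses in 12 of 13 subjects. It also leaves out Day 8 infusions under Table 4 and daily pazopanib.
- **Rewording 9a to match the calendar** would remove the inconsistency. It would do so by dropping the safeguard.
- **The wrong cross-reference is clerical.** Footnote g names its population in words, so no site should be misled.

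**Conclusion.** The concern holds. Inclusion 9a commits subjects to pregnancy testing during the study, and the protocol schedules none between first dose and EOT on either dosing schedule. The count of zero needs no assumption. The 8 Day 1 infusions without a scheduled test rest on 26 weeks of treatment in 21-day cycles without delay. The safety effect is modest because other safeguards remain, and no statistical result changes. The correction is desirable but minor. The Inclusion 5 reference is a separate clerical error and adds no weight to the finding.

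**What to change.** Add a urine (or serum) pregnancy test for women of child-bearing potential to the Day 1 column of Tables 4 and 5, to footnote g and to the Section 5.2.1 list. A workable choice is pre-dose on Day 1 of each cycle from Cycle 2, with the sponsor-investigator setting the final interval. A positive urine result should be confirmed by a serum test before dosing. Table 5 matters most because it governs new enrolments. The Table 4 cohorts are closed, so that change serves only subjects still on that schedule. In the same amendment, correct footnote g in both tables to refer to Inclusion 9.

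The documentary cost is one entry per table, one footnote edit in each and one line in Section 5.2.1. In conduct, urine is already collected on Day 1 for urinalysis, and the timing fits an existing allowance: "All Day 1 laboratory assessments and physical examination for Cycle 2+ may be performed up to 72 hours prior to planned treatment". The remaining cost is the test itself and an occasional false positive, which needs serum confirmation and may briefly delay a dose. Sample size and analysis are unaffected.
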